The microfluidic sperm sorting device has been shown to isolate highly motile, morphologically normal, and high DNA integrity sperm from unprocessed human semen. We have utilized the microfluidic sperm chip to select sperm for intracytoplasmic sperm injection (ICSI) in 26 cases of patients with poor prior ART outcome after standard sperm processing and selection. In these poor prognosis cases, we had 73% fertilization rate and 59% good quality day 3 embryos. Furthermore, among those patients who have received an embryo transfer, 58% (7 out of 12) have had a positive pregnancy test. While we cannot compare these data statistically to the prior failed cycle (due to concerns regarding regression to the mean), these data compare favorably to age-matched controls. However, given that this is a highly selected population, we believe a randomized controlled trial is necessary to rigorously explore the utility of sperm selection with the microfluidic sperm chip.

Hypothesis:

Subjects randomized to sperm preparation by microfluidic sperm sorting will obtain higher quality day 3 embryos than those randomized to traditional sperm processing.

Study Aims:

- 1) Primary Aim: To compare day 3 embryo quality resulting from fertilization of oocytes by sperm selected by microfluidic sperm sorting compared to traditional sperm preparation methods.
- 2) Secondary Aim: To compare fertilization rates, blastulation rates, and pregnancy rates for subjects randomized to sperm selection by microfluidic sperm sorting compared to traditional sperm preparation methods.

Design:

This is a randomized controlled trial of couples undergoing in vitro fertilization for unexplained infertility. Couples will be randomized to sperm selection by the clinical standard of centrifugation

and density-gradient processing compared to the microfluidic sperm sorting chip. Subjects and investigators performing outcome assessment will be blinded to treatment assignment.

Inclusion Criteria:

The target population includes couples planning in vitro fertilization (IVF) with or without intracytoplasmic sperm injection for unexplained infertility at the UCSF Center for Reproductive Health with a history of poor embryo quality as defined by $\leq 40\%$ high quality D3 embryos in a prior IVF cycle. All eligible couples will be asked to join the study.

Exclusion Criteria:

Male partner with severe oligoasthenospermia (concentration $< 5 \times 10^6$ spermatozoa/mL; motility $< 10\%$)

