As this is a randomized controlled trial, known and unknown confounders are assumed to be evenly distributed between treatment groups. However, at the completion of enrollment, baseline characteristics will be assessed between groups and chi squared or t-tests will be performed, as appropriate to ensure groups are evenly distributed with respect to the most important clinical parameters such as age, duration of infertility, gravity/parity, prior infertility treatment, and ovarian reserve (AFC). The primary outcome, day 3 high quality embryo proportion will be defined as proportion of all viable embryos on day 3 with at least 6 cells and fragmentation/symmetry scores of 1-2. This proportion will be compared between groups with a t-test. An ANOVA will be performed to obtain and age and AFC-adjusted comparison of day 3 high quality embryo proportion between groups. Secondary outcomes will include fertilization and pregnancy rates. Fertilization rate will be defined as number of 2PN embryos per oocyte retrieved. Pregnancy rate will be defined as clinical pregnancy (ultrasound demonstrating gestational sac with yolk sac) per transfer. These secondary outcomes will be evaluated with a t-test.

References:

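### Does leaving the unit of analysis unnamed for the day 3 quality and fertilization t-tests call for a change to the plan?

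*Combined protocol and SAP*

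**What the plan says.** All of the analysis text is in Statistical Methods of the combined protocol and SAP. The primary outcome is the "proportion of all viable embryos on day 3 with at least 6 cells" and good fragmentation and symmetry scores. The test follows directly: "This proportion will be compared between groups with a t-test". The adjusted analysis reads "An ANOVA will be performed to obtain and age and AFC-adjusted comparison of day 3 high quality embryo proportion between groups".

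For the secondary outcomes, "Fertilization rate will be defined as number of 2PN embryos per oocyte retrieved" and "Pregnancy rate will be defined as clinical pregnancy (ultrasound demonstrating gestational sac with yolk sac) per transfer". Then: "These secondary outcomes will be evaluated with a t-test".

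The unit of randomization is in Design: "Couples will be randomized to sperm selection by the clinical standard of centrifugation" or to the sorting chip. The Hypothesis reads "Subjects randomized to sperm preparation by microfluidic sperm sorting will obtain higher quality day 3 embryos than those randomized to traditional sperm processing". Inclusion Criteria defines poor embryo quality by a single proportion, at most 40% high quality, from a prior cycle. Study Procedures places randomization at the start of ovarian stimulation.

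No section says that the proportion is calculated once per couple, mentions clustering, or says what happens to a randomized couple with no oocyte or no viable day 3 embryo. Sample size, significance level, embryo and oocyte counts and within-couple correlation are not given.

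**The concern.** Embryos from one couple share the same gametes, stimulation and laboratory day, so their outcomes are likely to be positively correlated. If the t-test were run over individual embryos or oocytes scored 0 or 1, the standard error would be too small and the primary result could look significant too often. The definitions, worded over all viable embryos and per oocyte, leave room for that reading. The choice of a t-test does not settle the matter, because the same section applies a t-test to pregnancy per transfer, which is a yes/no outcome.

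A second gap remains even with the couple as the unit. A couple randomized at the start of stimulation may end with nothing to grade, so its proportion is 0/0. Excluding such couples or scoring them as 0% could give different answers if their share differed by arm.

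**Working it through.** **Step 1: which unit does the text imply?** Four features point to the couple.
- The variable compared is a proportion. A single embryo has a 0/1 score, not a proportion.
- The adjusting variables, female age and antral follicle count, take one value per couple.
- The hypothesis is about randomized subjects.
- Eligibility uses one proportion per prior cycle, so the authors already treat this measure as a couple-level quantity.

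Two features are neutral or point the other way: the t-test on pregnancy, and the Preliminary Studies percentages (73% fertilization, 59% good quality embryos over 26 cases), given without saying how they were averaged.

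**Step 2: error of each reading.** The plan has no figure to reproduce, so all inputs here are assumed. Take m embryos or oocytes per couple, within-couple correlation ICC, and a two-sided 5% level.
- Design effect: DE = 1 + (m − 1) × ICC.
- Error of a test that ignores couples: 2 × [1 − Φ(1.96 / √DE)].
- Example, m = 6 and ICC = 0.10: DE = 1 + 5 × 0.10 = 1.50; 1.96 / √1.50 = 1.60; error 11.0%.

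| ICC | DE, m = 6 | error | DE, m = 10 | error |
|---|---|---|---|---|
| 0.05 | 1.25 | 8.0% | 1.45 | 10.4% |
| 0.10 | 1.50 | 11.0% | 1.90 | 15.5% |
| 0.20 | 2.00 | 16.6% | 2.80 | 24.1% |
| 0.30 | 2.50 | 21.5% | 3.70 | 30.8% |

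A beta-binomial simulation under no effect let the counts vary between couples (4,000 runs per setting; 30, 60 and 120 couples per arm; at least one embryo or oocyte per couple). The ranges are over the three sample sizes.

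| ICC | per-embryo test (mean about 6, rate 40%) | per-oocyte test (mean about 10, rate 65%) |
|---|---|---|
| 0.05 | 9.8–10.1% | 11.9–13.5% |
| 0.10 | 13.4% | 18.9–19.9% |
| 0.20 | 21.4–22.2% | 28.2–29.1% |
| 0.30 | 26.1–27.0% | 36.1–36.8% |

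The t-test on one proportion per couple gave 4.3% to 5.5% over all 24 settings. The Monte Carlo standard error at 5% is √(0.05 × 0.95 / 4000) = 0.34 points, so this agrees with the nominal level.

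**Step 3: would a clustered model be better?** Power was compared for 60 couples per arm, 40% against 55%, a mean of 5.5 embryos and ICC from 0.05 to 0.30. From the couple-level t-test to a GEE clustered on couple, power moved from 88 to 92% down to 66 to 67% when the count SD was 2.3, and from 80 to 91% down to 62 to 66% when it was 3.9. The gain is therefore 1 to 4 points with modest variation in counts and 4 to 11 points with wide variation, largest at low ICC. The price is that the GEE gives more weight to couples with more embryos. If benefit rose by 1 point per extra embryo but averaged zero over couples, the GEE difference would be 0.3 to 1.8 points, against 0.0 to 0.1 for the couple-level test.

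**Step 4: couples with no viable embryo.** Assume a true rate of 40% in both arms.
- Shares of 10% and 2%, scored as 0%: 0.98 × 40 − 0.90 × 40 = 39.2 − 36.0 = 3.2 points in favour of the arm with fewer such couples.
- Shares of 20% and 5%, scored as 0%: 0.95 × 40 − 0.80 × 40 = 38.0 − 32.0 = 6.0 points.
- Excluded, and unrelated to quality: 0.0 points.
- Excluded, all from the lower-quality half: 0.7 to 2.1 points (10% and 2%) or 1.7 to 4.6 points (20% and 5%) in favour of the arm with more such couples.
- Equal shares of 5%: no shift.

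**The case for a change.** The strongest case for a change is that this is the primary endpoint, an embryo-level test is not expressly ruled out, and one sentence would close the gap before data are seen. The t-test on pregnancy shows that the authors do not reserve the test for continuous couple-level values. The inflation needs only positive correlation and more than one embryo per couple, and it does not shrink as the trial grows. Having the couple as the unit does not fully protect the level either: with 20% against 5% of couples lost, all from the lower-quality half, simulated rejection with those couples excluded ranged from 5.8% to 10.4%.

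What stands is that the text is silent on both points. The inflation figures, though, belong to a reading that the document leans against. The pregnancy test is a separate choice and says nothing about embryos as the unit.

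The loss scenarios are also stretched. Under Study Procedures, clinician and subject are blinded, the andrology laboratory learns the allocation on the day of trigger, and semen is processed after retrieval. Cancelled cycles and empty retrievals can therefore differ between arms only by chance. Failed fertilization and arrest before day 3 can respond to treatment, but nothing in the document supports shares such as 20% against 5%. The larger shifts, 3.2 and 6.0 points, come from scoring absent embryos as 0%. That answers a different question and is not bias in the planned comparison.

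**Conclusion.** No change is needed. Read as a whole, the plan compares one proportion per couple, and on that reading the t-test holds its 5% level (4.3% to 5.5% simulated). The error rates of 10% to 37% apply only to a per-embryo or per-oocyte test that the text does not naturally describe, and they rest on assumed counts and correlations. A clustered model is a fair alternative, but it gains little unless correlation is low and counts vary widely, and it changes which couples drive the estimate. The planned test also fits a hypothesis about subjects.

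The missing rule for couples with no viable embryo is ordinary detail. A competent analyst would compare couples with at least one, and report the others by arm and by stage, separating losses before sperm processing from those after it. The primary comparison would be the same with the rule written down. This conclusion assumes that the analyst takes the couple as the unit and that losses after sperm processing do not differ greatly between arms. A results report would show whether either assumption failed.

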Sperm Selection by Microfluidic Separation Improves Embryo Quality

NCT03085433

Document Date: 3/17/2017

Title: Microfluidic Separation Reduces Sperm DNA Damage and Improves Embryo Quality

Background/Significance

More than 70 million couples worldwide are infertile and up to 40 million are actively seeking infertility care. In the year 2013, a total of 160,521 assisted reproductive technology (ART) procedures were performed in the United States (Sunderam *et al*, 2015). Isolation of motile and morphologically normal sperm is an integral part of assisted reproduction. Traditional sperm processing for assisted reproduction involves centrifugation and “swim up” techniques that employ a density gradient to isolate motile sperm. However, studies have suggested that centrifugation induces reactive oxygen species and DNA damage (Malvezzi *et al*, 2014; Wang *et al*, 2014). Increased sperm DNA damage has been associated with poor outcomes in assisted reproduction, including lower fertilization rates, impaired embryo progression, and decreased pregnancy rates (Virro *et al*, 2004; Benchaib *et al* 2007; Simon *et al* 2014).

In contrast, microfluidic-based sperm sorting has the capability of selectively isolating highly motile, morphologically normal sperm with high DNA integrity from an unprocessed semen sample (Shirota *et al* 2016; Asghar *et al*, 2014; Tasoglu *et al* 2013). In semen samples from healthy male volunteers split into standard processing via centrifugation and swim-up procedure compared with microfluidic sperm sorting, a significantly higher percent motility and lower rate of sperm DNA fragmentation was detected with microfluidic sperm sampling (Shirota *et al* 2016). While the microfluidic sperm sorting technique has thus proven to be an efficient and reliable means of sperm preparation compared with the centrifugation and swim-up procedure, its use in clinical practice has not been rigorously studied. We aim to compare traditional preparation and microfluidic sperm sorting on assisted reproductive technology outcomes including oocyte fertilization and embryo quality in subjects electing to undergo in vitro fertilization for infertility.

Preliminary Studies:

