Female partner with anovulation (PCOS, FHA)

Female partner age > 41

Female partner AFC < 7

Female partner with obstructed fallopian tubes (assessed in all patients prior to IVF)

Use of oocyte donor

Either Partner:

Cancer diagnosis in either partner

Any significant disease or psychiatric disorder that would interfere with consenting process

Treatment History:

History of > 1 prior cycle cancellation due to poor response

Treatment Plan:

Embryo co-culture

Use of adjunctive non-gonadotropin medications to improve embryo quality: growth hormone, sildenafil

Study Procedures:

Couples meeting eligibility criteria will be offered enrollment. Randomization will be performed by the study coordinator upon initiation of controlled ovarian stimulation. Neither study clinician nor subject will be aware of treatment allocation. Ovarian stimulation will be performed with standard treatment chosen by primary physician. The day of ovulation trigger will be determined by the primary physician. The andrology lab will be notified of allocation to conventional sperm preparation versus microfluidic sperm sorting on the day of ovulation trigger. Oocyte retrieval is performed 36 hours after ovulation trigger. On the day of oocyte retrieval, the male partner will produce a semen sample per usual clinic protocol. A semen analysis will be performed on all samples for assessment of volume, motility, concentration, and morphology prior to semen processing according to WHO criteria using a light microscope, consistent with usual clinic protocol. Following the semen analysis, the semen of those assigned to microfluidic sperm sorting will be pipetted into the inlet chamber of the sorting chip. The microfluidic sperm sorting device is a flow and chemical-free microfluidic single use "chip" with an inlet sample chamber connected to an outlet collection chamber by a microfluidic channel. The sorted sperm are collected from the outlet.

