The semen of those assigned to standard processing will undergo conventional centrifugation and density gradient separation. ICSI or IVF will be performed by an embryologist blinded to treatment allocation with the processed sperm according to the primary physician's orders. After 16-18 hours, fertilization will be evaluated by the existence of two pro-nuclei. Fertilized embryos will be cultured to day 3 and evaluated by an embryologist blinded to treatment allocation for embryo quality. Cell number will be assessed in addition to blastomere symmetry and fragmentation (grade 1-6, highest quality to lowest). Those whose treatment plan involves a day 3 embryo transfer (determination made by primary physician) will undergo embryo transfer per clinic standard on day 3. Otherwise, embryos will be cultured to the blastocyst stage prior to

transfer. Blastocysts will be graded by Gardner Criteria, per clinic protocol. All women who undergo an embryo transfer will have a serum pregnancy test (beta HCG) 14 days later. Those with a positive serum test will repeat testing 48 hours later. Pregnancy ultrasounds will be scheduled at 5 weeks 5 days per clinic standard of care.

Device:

FERTILE: microfluidic sperm sorter

The device is labware. It is not an implant and is not purported to support or sustain human life. It is a flow and chemical free microfluidic single-use chip with an inlet chamber for receiving untreated semen samples and an outlet for collection of normal, healthy sperm for use in assisted reproductive technology procedures in andrology and embryology laboratories. It does not present any potential for serious risk to the health, safety, or welfare of participants.

Statistical Methods:

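### Clinical pregnancy is defined only per transfer, a denominator formed after the allocated sperm preparation, so couples without a transfer drop out and the arms compared may be selected groups

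*Combined protocol and SAP*

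**What the plan says.** The order of events is set out in Study Procedures. Allocation comes first: "Randomization will be performed by the study coordinator upon initiation of controlled ovarian stimulation". The laboratory learns of it later: "The andrology lab will be notified of allocation to conventional sperm preparation versus microfluidic sperm sorting on the day of ovulation trigger". The allocated preparation is applied to the semen sample on the day of oocyte retrieval. Fertilization, culture to day 3 or blastocyst, and transfer follow. Pregnancy is then ascertained among those with a transfer: "All women who undergo an embryo transfer will have a serum pregnancy test (beta HCG) 14 days later", and "Pregnancy ultrasounds will be scheduled at 5 weeks 5 days per clinic standard of care".

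Statistical Methods defines the outcome: "Pregnancy rate will be defined as clinical pregnancy (ultrasound demonstrating gestational sac with yolk sac) per transfer". No section gives a rate per randomized couple, per started cycle or per retrieval. There is no intention-to-treat statement and no rule for couples who have no transfer. Yet the secondary aim under Study Aims is worded as a comparison of pregnancy rates in couples as randomized.

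**The concern.** Whether a couple enters the pregnancy analysis is decided after the allocated preparation has been used. The protocol's own rationale gives a reason why the preparation could affect that step. Background/Significance states: "Increased sperm DNA damage has been associated with poor outcomes in assisted reproduction, including lower fertilization rates, impaired embryo progression, and decreased pregnancy rates". Poor fertilization and poor embryo progression both come before transfer and can prevent it. The Hypothesis expects better day 3 embryos with the chip, and the Inclusion Criteria select couples with poor embryo quality in an earlier cycle, for whom a cycle without a transferable embryo is plausible.

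If the chip changes who reaches transfer, the per-transfer comparison can differ in size, or even in sign, from the effect on a couple's chance of pregnancy. It can go against the chip, by adding weaker transfers to that arm, or in its favour, by removing them. Losses before sperm processing, such as a cancelled stimulation, cannot be caused by the device. The concern is with losses after it.

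**Working it through.** **The plan's own figures.** The plan gives no sample size, assumed pregnancy rate or transfer share, so there is no design figure to reproduce. The only relevant data are in Preliminary Studies, where the chip was used "in 26 cases of patients with poor prior ART outcome after standard sperm processing and selection" and, "among those patients who have received an embryo transfer, 58% (7 out of 12) have had a positive pregnancy test".

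- Per patient with a transfer: 7/12 = 58.3%, which agrees with the stated 58%.
- Share with a transfer: 12/26 = 46.2%.
- Per case: 7/26 = 26.9%.

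This shows how far the denominator can move the figure. It does not estimate bias. The series has one arm, the outcome is a positive test rather than clinical pregnancy, the text counts cases in one place and patients in the other, and some of the remaining 14 may still have been awaiting transfer.

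**Model.** Let r0 and r1 be the shares of randomized couples reaching transfer in the standard and chip arms, with at most one transfer per couple. Let the standard arm have 30% clinical pregnancy per couple, and let s be the success rate of the transfers that the chip adds or removes. The chip is assumed to change reach only. All these rates are assumptions.

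- Chip, per couple = 0.30 + (r1 - r0) x s
- Per-transfer gap = (chip per couple)/r1 - 0.30/r0

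Example, 75% v 85% with s = 10%: chip per couple = 0.30 + 0.10 x 0.10 = 0.31. Per transfer, 0.31/0.85 = 36.5% against 0.30/0.75 = 40.0%, a gap of -3.5 points, while the per-couple difference is +1.

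| Reach, standard v chip | s | Chip per couple | Per transfer, standard v chip | Per-transfer gap (points) | Per-couple difference (points) |
|---|---|---|---|---|---|
| 80% v 85% | 0% | 30.0% | 37.5% v 35.3% | -2.2 | 0 |
| 80% v 85% | 10% | 30.5% | 37.5% v 35.9% | -1.6 | +0.5 |
| 80% v 85% | 20% | 31.0% | 37.5% v 36.5% | -1.0 | +1.0 |
| 75% v 85% | 0% | 30.0% | 40.0% v 35.3% | -4.7 | 0 |
| 75% v 85% | 10% | 31.0% | 40.0% v 36.5% | -3.5 | +1.0 |
| 75% v 85% | 20% | 32.0% | 40.0% v 37.6% | -2.4 | +2.0 |
| 75% v 85% | 40% | 34.0% | 40.0% v 40.0% | 0 | +4.0 |
| 75% v 90% | 0% | 30.0% | 40.0% v 33.3% | -6.7 | 0 |
| 75% v 90% | 10% | 31.5% | 40.0% v 35.0% | -5.0 | +1.5 |
| 75% v 90% | 20% | 33.0% | 40.0% v 36.7% | -3.3 | +3.0 |
| 85% v 75% | 10% | 29.0% | 35.3% v 38.7% | +3.4 | -1.0 |
| 85% v 75% | 20% | 28.0% | 35.3% v 37.3% | +2.0 | -2.0 |

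The rows with s = 0 are the largest gaps within this model at 30% per couple. They are not general limits: at 40% per couple, 75% v 85% gives 0.40/0.85 - 0.40/0.75 = 47.1% - 53.3% = -6.3 points. In the s = 40% row the added transfers succeed at the standard per-transfer rate. The per-transfer gap is then zero and a 4-point gain per couple is missed. The two 85% v 75% rows are the mirror case, in which the chip loses weak transfers and looks better than it is.

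**A second set of assumptions.** Suppose 70% reach transfer in either arm and 45% of them conceive, and the chip brings a further 10 to 20% of couples to transfer, of whom 20% conceive.

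- Per transfer, chip: (0.70 x 0.45 + 0.10 x 0.20)/0.80 = 41.9%, down to (0.70 x 0.45 + 0.20 x 0.20)/0.90 = 39.4%, against 45.0%.
- Per couple, chip: 33.5% to 35.5%, against 0.70 x 0.45 = 31.5%.

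The sign reverses here too.

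**The case against.** The strongest objection is that the sign reversal needs the chip to change reach and nothing else, whereas the trial's hypothesis is that it improves embryos. With 75% v 85% and s = 10%, a gain of 4 points among couples who would have had a transfer anyway removes the negative gap: 0.75 x 0.44 + 0.10 x 0.10 = 0.34, and 0.34/0.85 = 40%, equal to the standard arm. That stands as a limit on how readily the reversal would appear. It does not rescue the definition, because the per-couple gain in that example is 34% - 30% = 4 points and the per-transfer comparison shows none of it.

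The pilot is weak evidence that many couples will have no transfer, for the reasons given with it. The exclusions for low AFC, female age, repeated cancellation for poor response and severe oligoasthenospermia plausibly reduce such cycles, although the poor-embryo-quality entry criterion pulls the other way.

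Blinding of clinicians and embryologists limits differential decisions about transfer, and fertilization and blastulation are to be compared in their own right. Blinding does not remove a biological effect of the preparation on which embryos survive, and the separate comparisons do not restore a randomized denominator.

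Finally, the gaps may be small beside the sampling error. Assuming 40 to 160 transfers per arm at 37.5%, the standard error of the difference, the square root of 2 x 0.375 x 0.625/n, runs from 10.8 down to 5.4 points. The 1 to 5 point gaps at s = 10 to 20% lie below one standard error throughout. That limits the practical effect but is no reason to keep an avoidable bias.

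**Conclusion.** The concern holds. The only pregnancy denominator in the plan is formed after the allocated preparation, and it does not match the stated aim of comparing couples as randomized. Confidence is high on the definition and its consequence for the comparison, but not on the size of any bias, which the documents do not allow to be estimated. Under the assumed rates with s = 10 to 20%, the per-transfer gap runs from -5.0 to -1.0 points where the chip adds transfers, while the true per-couple difference is +0.5 to +3. In the mirror case it is +2.0 to +3.4 while the true difference is -2 to -1. If reach is equal and the same kind of couple reaches transfer in both arms, there is no bias.

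The point concerns one secondary outcome and should be corrected. The pregnancy definition does not enter the primary analysis. The primary outcome's own denominator, viable day 3 embryos, is a separate question that is not judged here.

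**What to change.** Replace the pregnancy definition in Statistical Methods with wording such as: *clinical pregnancy (existing ultrasound definition) from the study-cycle transfer described in Study Procedures, per randomized couple, by allocated arm; couples with no transfer count as not pregnant; risk difference with 95% CI.*

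In addition:

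- As a sensitivity analysis, use couples whose oocytes were retrieved, a denominator fixed before sperm processing. If 90% are retrieved in both arms (assumed), 30% v 32% per randomized couple becomes 0.30/0.90 = 33.3% v 0.32/0.90 = 35.6%, a difference of +2.2 instead of +2.0 points, with the same sign.
- Report the numbers randomized, retrieved and transferred by arm.
- Keep the per-transfer rate as a descriptive figure.
- If later transfers from the same retrieval are to count, fix the window before unblinding.

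Removing the bias needs no change of test and no change to clinical management. For the study-cycle transfer the cost is SAP wording and the by-arm counts, since the pregnancy test and ultrasound are already planned. There are three downsides. The reported rate will be lower. Cancellations before retrieval dilute the difference, hence the sensitivity analysis. Couples whose transfer is deferred count as not pregnant, which would misstate the eventual chance of pregnancy if deferral differed by arm. Counting later transfers would address this last point, but it may need follow-up that Study Procedures does not describe.

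### Clinical pregnancy, a yes/no outcome, is assigned a t-test with no stated adjustment for age and AFC and no stated effect measure; the loss is modest precision and a missing interval, not false-positive control

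*Combined protocol and SAP*

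**What the plan says.** All of the relevant text is in the combined protocol and SAP.

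- **Outcome (Statistical Methods).** "Pregnancy rate will be defined as clinical pregnancy (ultrasound demonstrating gestational sac with yolk sac) per transfer".
- **Test (Statistical Methods).** For fertilization and pregnancy together: "These secondary outcomes will be evaluated with a t-test". No covariates, effect measure or interval are named.
- **Adjustment (Statistical Methods).** It is written for the primary outcome only: "An ANOVA will be performed to obtain and age and AFC-adjusted comparison of day 3 high quality embryo proportion between groups".
- **Test by data type (Statistical Methods).** For baseline comparisons, "chi squared or t-tests will be performed, as appropriate". Chi-squared is mentioned nowhere else, and no method for a binary outcome is named for pregnancy.
- **Availability of the covariates.** Both are exclusion criteria ("Female partner age > 41" and "Female partner AFC < 7"), and both appear in the list of key baseline characteristics. They are therefore known for every couple before randomization.
- **Timing (Study Procedures).** Randomization takes place when ovarian stimulation starts. Transfer comes later, after retrieval, fertilization and embryo culture.

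The document states no sample size, significance level, power or expected clinical pregnancy rate.

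**The concern.** A t-test compares means, and clinical pregnancy is present or absent. The plan matches test to data type at baseline but not for the clinical outcome that patients will look for first. It also treats age and AFC as important enough to adjust the primary outcome, then gives no reason for leaving them out of the pregnancy comparison.

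Three things are at stake. The first is precision, if age and AFC predict pregnancy. The second is an interpretable result: a t-test p-value alone does not tell a reader how large a difference in pregnancy the data allow. The third is the denominator: a per-transfer rate compares only couples who reached a transfer, which is decided after randomization.

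**Working it through.** The plan has no design figure of its own to reproduce. Everything below assumes two-sided 5%, 1:1 allocation and one transfer per couple, over a range of sizes and rates.

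**1. Is the t-test itself a problem?** With n transfers per arm and observed proportions p1 and p2:

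- Pooled variance: s² = n[p1(1−p1) + p2(1−p2)] / (2n−2)
- t = (p2−p1) / √(2s²/n), on 2n−2 degrees of freedom
- Pearson: z = (p2−p1) / √(2p̄(1−p̄)/n), where p̄ = (p1+p2)/2
- The two are linked by z² = 2n·t² / (t² + 2n − 2)

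Example, 12/40 v 20/40. s² = 40(0.21 + 0.25)/78 = 0.236, the standard error is 0.109, and t = 0.20/0.109 = 1.84, so p = 0.069. For Pearson, z = 0.20/√(2 × 0.24/40) = 1.83, so p = 0.068. Check: 80 × 3.391/(3.391 + 78) = 3.33 = z².

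Enumerating all possible tables at the 5% level:

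- The tests never disagree at 10 to 40 per arm. They disagree on 4 of 2,601 tables at 50 and 4 of 10,201 at 100.
- For true rates of 10% to 50%, exact type I error of the t-test is 0.9% to 4.2% at 10 per arm and 2.5% to 6.5% at 15 to 40 per arm (maximum at 25 per arm and a 50% rate).
- For 30% v 50% at 100 per arm, power is 83.2% by either test.

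**2. When is the t-test undefined?** When nobody is pregnant, which has probability (1−p)^(2n). At 10 per arm this is 0.9^20 = 12% for a 10% rate, 0.8^20 = 1.2% for 20%, and 0.7^20 = 0.08% for 30%.

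**3. What does adjustment gain?** The model is logit P(pregnant) = b0 + b1·arm + b2·age + b3·AFC, with standardized covariates. Power from simulation at 60 per arm, treatment log odds ratio 1.0:

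| Assumed log-odds per SD (age/AFC) | t-test | Adjusted logistic | Change (points) |
|---|---|---|---|
| not prognostic | – | – | about −1 |
| 0.4/0.2 | 76% | 78% | +2 |
| 0.6/0.3 | 71% | 74% | +3 |
| 0.9/0.5 | 61% | 69% | +8 |

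Simulation error is about 0.8 points per power figure with 3,000 runs: √(0.75 × 0.25/3000). Separate runs gave gains of 0 to 1 points in the weakest prognostic case and 7 to 8 in the strongest.

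A second set used log odds ratio 0.85:

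| Per arm | Not prognostic | 0.5/0.3 | 0.8/0.5 |
|---|---|---|---|
| 50 | 57.4% → 55.2% | 49.9% → 50.7% | 43.6% → 47.5% |
| 100 | 84.3% → 83.6% | 77.9% → 80.0% | 72.6% → 77.8% |

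The change therefore runs from about −2 to +5 points in this set.

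**4. Is the adjusted model safe in small samples?** Under no effect, with a pregnancy rate of about 23% to 25%, the adjusted logistic likelihood-ratio test rejects in about 11% to 12% of trials at 10 per arm and 6% to 8% at 15 to 20. The t-test rejects in 4% to 5%. The logistic test is near nominal by 40 to 60 per arm.

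**5. Would an event threshold prevent that?** Counting arm, age and AFC as three parameters, 10 per parameter requires 30 pregnancies and 30 non-pregnancies. At 20 per arm there are 40 couples, so the smaller count is at most 20 and the unadjusted analysis always applies. At 60 per arm with 35% in controls and odds ratio e^1.0, the other arm's rate is 1.464/2.464 = 59%. Expected pregnancies are then 21 + 36 = 57 of 120, and the model is used.

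**The case against.** The strongest reply is that the stated test changes almost nothing. It decides as chi-squared would, its mean difference is already the unadjusted risk difference, and its usual interval would serve as a 95% CI. An unadjusted randomized comparison is valid, so adjusting a secondary outcome is a preference. The larger gains need strong covariates, in a population already restricted on age and AFC. All of this stands, and it is why the point is limited to precision and reporting. It does not explain why the plan adjusts one outcome and not the other, and the interval that the t-test could supply is not promised.

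It also stands that a careless replacement would be worse. An adjusted logistic likelihood-ratio test without a threshold rejects too often in small samples. Fisher's exact test is conservative: for 30% v 50% at 40 per arm, its power is 37% against 46% for the t-test.

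A reader might infer several stronger criticisms that the document does not support:

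- **That the t-test inflates false positives or is unusable.** Steps 1 and 2 show otherwise. The undefined case needs about 10 per arm and a 10% rate, and with no pregnancies chi-squared is undefined and the logistic model cannot be fitted either.
- **That pregnancies will be few.** No sample size or expected rate is given. The only related figure, 7 of 12 (58%) in Preliminary Studies, counts positive tests in an uncontrolled series, not clinical pregnancies.
- **That repeat transfers break independence.** Study Procedures describes one stimulation, one retrieval, one transfer and a pregnancy test afterwards. No second transfer is mentioned.

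**Conclusion.** The point holds in a limited form. The plan assigns a t-test to a binary outcome, writes no adjustment for it although age and AFC are in hand, and names no risk difference with an interval. That the pregnancy comparison is unadjusted is inferred from silence, but adjustment is spelled out for the primary outcome alone, so the inference is sound.

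The cost is about -1 to +8 power points at an assumed 60 per arm, and -2 to +5 in the 50 and 100 per arm settings, plus a less informative result. These figures are for tests of the odds ratio in a logistic model. They rest on assumed rates, effects and covariate strengths, because the document supplies none.

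Changing the model does not cure the per-transfer denominator, which still conditions on an event after randomization. For a secondary outcome this is a cheap, worthwhile improvement and not a threat to the trial's validity.

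**What to change.** Replace the t-test for pregnancy with the following, and fix it before unblinding:

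1. **Unit.** One observation per couple: clinical pregnancy yes or no from the study cycle's transfer.
2. **Model and estimate.** Adjust for age and AFC and report the adjusted risk difference with a 95% CI, either by standardizing a logistic regression or by linear regression on the 0/1 outcome with robust standard errors. Name one of the two, and the form of standard error, in advance.
3. **Threshold.** State a count below which the unadjusted risk difference with its interval and a chi-squared or exact test is used instead. One example is fewer than about 10 pregnancies or 10 non-pregnancies per model parameter, saying which parameters are counted.
4. **Denominator.** Also report pregnancy per randomized couple, and state how couples without a transfer are counted.

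The t-test can stay for the per-couple fertilization proportion.

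The cost is a few sentences and slightly more analysis work, with no new data. If age and AFC turn out not to be prognostic, adjustment loses about 1 to 2 power points. The threshold will also forgo adjustment in some trials where it would have been safe: 40 per arm at a 25% rate gives 20 pregnancies, below 30, although the adjusted test is near nominal there.
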